Duration of wear = Date of removal visit – Date of application visit – duration of study therapy interruption

If an unscheduled visit takes place between consecutive assessments multiple duration of wear values will be derived:

Duration of wear 1= Date of unscheduled visit – Date of application study visit

Duration of wear 2= Date of removal study visit – Date of unscheduled visit – duration of study therapy interruption

If more than one unscheduled visit occurs between consecutive assessments, further multiple wear times will be derived as above.

27. The average wear time per patient (patient level) will be derived as follows per subject:

Sum of duration of dressing wear (dressing level) values / Count of duration of dressing wear (dressing level) values

28. The median value for the baseline (Run-In Visit 2/Study Visit 1) target ulcer area will be derived for both the Full Analysis Set and Per Protocol populations by wound type and overall. The median value will also be derived for the depth and volume.

29. Whether or not the reference ulcer is clinically infected at any Study Visit.

30. Whether or not the reference ulcer has signs of infection at any Study Visit.

31. Whether an intervention was required will be derived for each subject:

If an unscheduled visit is recorded, where the reason for intervention is not given as routine: Intervention = Yes

If no unscheduled visits are recorded: Intervention = No

32. Whether prescription of an antibiotic was required will be derived for each subject:

If "have any systemic antibiotics been prescribed" = Yes at any assessment, or any antibiotic medications are recorded on the concomitant medications form, with a start date after randomization: Antibiotic = Yes

Document Number: 1004313

Document Version: 06

Document Part: 000

Document Status: Released

If "have any systemic antibiotics been prescribed" = No at all assessments, and no antibiotic medications are recorded on the concomitant medications form:
Antibiotic = No

33. Whether an intervention or prescription of an antibiotic was required will be derived for each subject:
If Intervention derivation (Derived Variable 31) = Yes or Antibiotic derivation (Derived Variable 32) = Yes, then need for intervention or antibiotic= Yes
If Intervention derivation (Derived Variable 31) = No or Antibiotic derivation (Derived Variable 32) = No, then need for intervention or antibiotic= No

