4.11 Exploratory Variables

Presence of Infection and Clinical signs of infection

A Fishers Exact test will be used to test for a difference in the percentage of subjects with incidence of infection presenting during the 12-week treatment period between treatments using the Full Analysis Set, the corresponding 95% confidence intervals will also be presented.

The presence of infection and clinical signs of infection will be summarized by regular Study Visit, at treatment discontinuation and, where appropriate at the one-week confirmation visit. Whether the reference wound is clinically infected at any post baseline assessment will also be summarised.

In addition, the summaries will be separated by reference wound filler used at baseline (gauze, foam or none).

Whether the reference wound has signs of clinical infection at any post baseline assessment and whether the reference wound has signs of clinical infection at treatment discontinuation will be cross tabulated against whether the reference wound has signs of clinical infection at baseline separately for each treatment.

Need for administration of antibiotics and additional interventions

A Fishers Exact test will be used to test for a difference in the percentage of subjects requiring either the administration of antibiotics or additional interventions, between treatments using the Full Analysis Set. The corresponding 95% confidence intervals will also be presented. Individually, Fishers Exact tests will be used to test for a difference in the percentage of subjects requiring the administration of antibiotics and additional interventions separately, between treatments.

The need for administration of antibiotics and additional interventions (and either intervention), and type of intervention will be summarized at per subject by treatment and wound type.

Dressing wear time

A linear regression model will be fitted to the average wear time per subject. Treatment, center, wound type, baseline ulcer area, baseline exudate level and baseline mobility level will be included in the initial model. The difference between the two treatments in terms of average wear time per subject (treatment parameter estimate) will be presented along with the 95% confidence intervals.

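### SAP 4.3 item 33 gives both Yes and No to every subject with one component Yes and the other No, so its No rule must be corrected together with the component definitions

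*SAP*

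**What the plan says.** Item 33 in SAP 4.3 states its purpose as follows: "Whether an intervention or prescription of an antibiotic was required will be derived for each subject". Two lines then define it:

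- Yes line: "If Intervention derivation (Derived Variable 31) = Yes or Antibiotic derivation (Derived Variable 32) = Yes, then need for intervention or antibiotic= Yes".
- No line: "If Intervention derivation (Derived Variable 31) = No or Antibiotic derivation (Derived Variable 32) = No", in which case the composite is set to No.

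The composite feeds a Fisher's exact test between arms in SAP 4.11, on the percentage of "subjects requiring either the administration of antibiotics or additional interventions", using the Full Analysis Set. Protocol 10.3.3 plans the same either/or comparison.

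The two components are items 31 and 32 of the same section. For interventions, the Yes condition is "If an unscheduled visit is recorded, where the reason for intervention is not given as routine: Intervention = Yes" and the No condition is "If no unscheduled visits are recorded: Intervention = No". For antibiotics, Yes needs a systemic antibiotic prescribed at any assessment, or an antibiotic on the concomitant medications form that started after randomization. No needs a negative answer at every assessment and no antibiotic of any date on that form.

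**The concern.** The opposite of needing at least one of two things is needing neither, so the No line should join its conditions with *and*. With *or*, it overlaps the Yes line for every subject who is Yes on one component and No on the other. Two programmers could both follow item 33 faithfully and produce different data. One who codes Yes first and treats No as the alternative gets the intended composite. One who codes two successive statements lets the second overwrite the first and gets a variable that is Yes only when both were needed.

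At stake are the composite's percentages, its confidence intervals and its Fisher test. Protocol 9.5 also makes a post-hoc health economic analysis depend on statistical differences in the exploratory or safety assessments, and this test is one of several that could set it off.

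**Working it through.** The plan states no figure for this composite, so there is nothing to reproduce. The check is a truth table, followed by arithmetic on assumed rates.

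**Step 1: apply both lines to every combination.** A dash in the first two columns means that item 31 or 32 assigns no value.

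| Intervention (31) | Antibiotic (32) | Yes line | No line | As written | No line with *and* only |
|---|---|---|---|---|---|
| Yes | Yes | fires | – | Yes | Yes |
| Yes | No | fires | fires | contradictory | Yes |
| No | Yes | fires | fires | contradictory | Yes |
| No | No | – | fires | No | No |
| – | Yes | fires | – | Yes | Yes |
| Yes | – | fires | – | Yes | Yes |
| – | No | – | fires | No | unassigned |
| No | – | – | fires | No | unassigned |
| – | – | – | – | unassigned | unassigned |

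Two of the four complete combinations are contradictory.

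**Step 2: share of true positives turned to No if the No line is applied last.** Let a and b be the intervention and antibiotic rates, with both components assigned for everyone. The share lost is 1 − P(both)/P(either), where P(either) = a + b − P(both). The documents give neither a, b nor the overlap, so all rates below are assumptions.

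Independent components, P(both) = ab:

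- 10%/10%: 1 − 0.01/0.19 = 95%
- 20%/25%: 1 − 0.05/0.40 = 87.5% (true composite 40%, returned 5%)
- 50%/50%: 1 − 0.25/0.75 = 67%
- 80%/80%: 1 − 0.64/0.96 = 33%

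Maximum overlap, P(both) = the smaller of a and b:

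- 20%/20%: 1 − 0.20/0.20 = 0%
- 30%/20%: 1 − 0.20/0.30 = 33%
- 30%/10%: 1 − 0.10/0.30 = 67%

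If the Yes line prevails, the share is 0% at any rates.

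**Step 3: where a component has no value.** Item 31 says nothing about a subject whose unscheduled visits were all routine. Protocol 9.1.7 has the interim dressing changes of tNPWT subjects, and of subjects with a filler, recorded as unscheduled visits, so such subjects are to be expected, mainly in the tNPWT arm. Item 32 says nothing about a subject whose only recorded antibiotic started before randomization.

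As an extreme illustration, suppose that every tNPWT subject has at least one routine unscheduled visit, with the independent 20%/25% rates and no gap in item 32. Item 31 is then Yes in 20% and unassigned in 80%, never No.

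- As written with the No line last, the composite is Yes exactly when item 32 is Yes: 25%, against a true 40%. A subject with an antibiotic only is classified correctly.
- With *and* alone, subjects with neither component, 0.80 × 0.75 = 60% of the arm, become unassigned, and every assigned tNPWT subject is a Yes.

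**The case against.** The strongest reply is that this is a drafting slip with an obvious meaning. The stated purpose of item 33, its Yes line, SAP 4.11 and Protocol 10.3.3 all describe an either/or composite, and a sensible programmer would code it so. SAP 4.11 also tests antibiotics and interventions separately, and those tests do not use item 33. All of this stands, and it is why the severity is low. It does not remove the contradiction, because a derivation should not need the programmer to choose which of its lines to ignore.

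Two stronger readings are tempting and are not supported. A reader might infer that most positive subjects are misclassified. That needs the No line to override the Yes line, which the SAP does not say, and it needs subjects positive on both components to be fewer than half of all positives, for which the documents give no figures. Overlap could be substantial, since a target ulcer infection may lead to both a non-routine visit and an antibiotic. A reader might also infer that everyone with an antibiotic alone is misclassified. That fails for subjects whose unscheduled visits were all routine: item 31 gives them no value, so only the Yes line fires.

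The objection that replacing one word is not a safe repair also stands. By itself, that change would leave subjects with only routine unscheduled visits and no antibiotic without a value, whereas the present wording correctly gives them No.

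**Conclusion.** Item 33 is wrong as written. The contradiction for subjects with one Yes and one No follows from the text and needs no assumption. Whether anyone is misclassified depends on which line is applied last, which the SAP leaves open. The share of positives affected then depends on unstated rates and overlap: from 0% to about 95% across the cases shown. Those percentages are illustrations, not estimates for this trial.

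Severity is low. One exploratory composite and its summary are affected; the primary and secondary endpoints do not use item 33.

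**What to change.** Amend three items of SAP 4.3 in one edit:

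1. Item 33: the composite is No only if derived variable 31 = No **and** derived variable 32 = No. The Yes line stays as it is.
2. Item 31: No if there are no unscheduled visits, or if all unscheduled visits are routine.
3. Item 32: No if no systemic antibiotic was prescribed at any assessment and no antibiotic on the concomitant medications form started after randomization.

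The cost is a few words in the SAP and the matching program lines, with no new data to collect. The first change should not be made without the other two, because it would then leave some true non-events unassigned, mostly in the tNPWT arm.

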This document contains confidential information, which is the property of Smith & Nephew, Inc. Do not copy, disclose, or circulate without written authorization from the appropriate Smith & Nephew personnel

CONFIDENTIAL DOCUMENT
This document contains confidential information, which is the property of Smith & Nephew, Inc. Do not copy, disclose, or circulate without written authorization from the appropriate Smith & Nephew personnel.

5. Remove NPWT topical dressing to assess the target ulcer.
6. Assess level of pain, post NPWT dressing removal, using the VAS.
7. Complete reason for dressing change assessment and record any additional dressing changes since previous assessment as an unscheduled visit.
8. Assess target ulcer and record if target ulcer is closed or if target ulcer is ready for and will be surgically closed.

Note 1: If the target ulcer is closed, skip procedures 9-15 and complete procedure 16.

Note 2: If target ulcer is ready for and will be surgically closed, skip procedures 9-16 and complete procedure 17.

9. Examine the ulcer for evidence of infection, and treat the infection as appropriate per local protocol.
10. Debride the ulcer if indicated, at the discretion of the Investigator.
11. If the target ulcer remains open, photograph and determine the post-debridement ulcer area (cm²), perimeter (cm), greatest depth (mm), volume (cm³), and maximum linear dimension (cm) using the ARANZ Silhouette wound imaging and measurement device if applicable.

If debridement is not performed, an image of the target ulcer is still required to determine the ulcer area (cm²), perimeter (cm), greatest depth (mm), volume (cm³) and maximum linear dimension (cm) using the ARANZ Silhouette wound imaging and measurement device.

12. Conduct an ulcer assessment using the modified Bates-Jensen wound assessment tool and record percentage tissue type/condition of peri-wound skin assessment (Normal, Erythematous, Edematous, Eczematous, Excoriated, Macerated, Indurated).
13. Re-application of investigational product (PICO) or comparator tNPWT system

according to randomization schedule.

Record any additional dressings used and rationale for using this dressing.

Type of wound filler dressing if used (foam or gauze-based filler dressing).

Number of personnel used to apply NPWT system.

Time used to apply NPWT system (minutes).

Record level of negative pressure, intensity setting and delivery mode selected for tNPWT subjects, if appropriate for device selected.

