9.1.7 Unscheduled Visits

Unscheduled exams may be conducted at the discretion of the Investigator with all obtained information recorded in the source documents and on the Unscheduled Visit pages within the Case Report Form (CRF) booklet.

Subjects using a negative pressure filler dressing or using tNPWT will be instructed to complete a dressing change in 2-3 days from application. This visit should be captured as an unscheduled visit.

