9.5 HEALTH ECONOMICS/QUALITY OF LIFE

The impact of, and comparison of, trial treatments on subject Quality of Life is included as a secondary study objective. Namely, the difference between treatments in the change in subject reported Quality of Life (QoL) during the 12-week treatment period.

The Health Related Quality of Life (HRQoL) will be assessed using the EQ-5D and CWIS validated instruments. Study subjects will complete both instruments at the Randomization Study Visit 1 and at the End of Treatment period.

Resource use will also be captured and detailed by treatment, including the following: material usage (number of dressing applied and additional materials used), personnel usage (number of personnel, and time, required for dressing change), additional interventions and hospital admissions. Should quantifiable statistical differences be observed in any of the exploratory or safety assessments, a post-hoc health economic analysis will be conducted. This post-hoc analysis will examine the economic implications of the observed differences in resource utilization between the PICO and tNPWT groups by applying existing market prices to the resources utilized and comparing total direct costs between the two groups.

Resource use, as detailed in the previous paragraph, will also separately be detailed by individual tNPWT device.

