34. All pain assessments (dressing removal, during wear, on initiation of therapy) will be derived as follows:
In cases where pain = No, the VAS pain value will be coded as 0
35. Level of Exudate (amount) will be coded as follows- In cases where Exudate presence=No, then the level/amount of exudate will be coded as None.
36. The responses to the aspects of the wound assessment tool (BWAT-M); Undermining, Necrotic Tissue Type, Necrotic Tissue Type, Necrotic Tissue Amount, Exudate Type, Exudate Amount, Skin Color Surrounding Wound, Granulation Tissue and Epithelialization will be coded at each study visit as defined in Section 7. The individual coded values will then be summed at each individual study visit to give a total wound status score.
37. The personnel time taken at each Study Visit will be derived as:
No. of personnel applying the dressing x time taken to apply the NPWT system
38. The total personnel time taken at throughout the study will be the sum of the personnel time at Study Visits per subject.
39. The duration for which compression therapy was interrupted at each Study Visit in hours will be derived as: hours + (daysx24). If no interruption is recorded then the number of hours will be coded as 0.

ST:

9 7 5

Reference:

CE/052/PIC

Customer Code:

0 5

40. The duration for which study therapy was interrupted at each Study Visit in hours will be derived as: hours + (daysx24). If no interruption is recorded then the number of hours will be coded as 0.
41. The total duration (in hours) for which compression therapy was interrupted per subject will be calculated as the sum of the interrupted duration at each Study Visit.
42. The total duration (in hours) for which study therapy was interrupted per subject will be calculated as the sum of the interrupted duration at each Study Visit.
43. In cases where the ulcer is recorded as closed in the investigators opinion the following imputations will be made if missing values are present:
- Presence of infection = No
 - Presence of clinical signs of infection = No
 - Level of Exudate = None/No
 - Extent of undermining = None
 - Necrotic tissue present = No
 - Epithelialization at target ulcer = 100% wound covered, surface intact
44. Individual flags for whether each event was a serious adverse event, severe adverse event, investigational device related adverse event, a serious investigational device related adverse event, an unexpected adverse event and a serious unexpected adverse event.

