In addition, the total personnel time taken (in minutes) to apply the NPWT system for each subject will be summarized by treatment. A two sample t-test will be used to test for a difference in the mean total time taken (in minutes) to apply the NPWT system between treatments. 95% confidence intervals will also be presented. If the assumptions of the t-test are violated, the Wilcoxon rank sum test will be used instead with Hodges-Lehmann estimates of the median difference and 95% confidence interval reported.

The number of personnel (and type of personnel) applying the device will be summarized overall Study Visits by treatment, and separated by intermittent/continuous, and by whether any filler dressing was used.

Continuing Dressing Usage

Whether any dressings were applied at Study Visit 14 will be summarized by treatment and by whether the ulcer is open / closed at Study Visit 14.

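### The SAP's total personnel time counts scheduled visits only, so the between-visit dressing changes instructed for tNPWT and filler users drop out of the tested total

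*SAP*

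**What the plan says.** SAP 4.3, item 37, defines personnel time at each Study Visit as "No. of personnel applying the dressing x time taken to apply the NPWT system". Item 38 adds these up: "The total personnel time taken at throughout the study will be the sum of the personnel time at Study Visits per subject". SAP 4.12, under Resource Use, tests the per-subject total: "A two sample t-test will be used to test for a difference in the mean total time taken (in minutes) to apply the NPWT system", with a Wilcoxon fallback. Under SAP 4.1 the test is two-sided at 5%.

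Protocol 9.1.7 creates planned dressing changes between the weekly visits: "Subjects using a negative pressure filler dressing or using tNPWT will be instructed to complete a dressing change in 2-3 days from application". It adds: "This visit should be captured as an unscheduled visit". Protocol 9.1.4 likewise has staff "record any additional dressing changes since previous assessment as an unscheduled visit".

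SAP item 26 keeps the two kinds of visit apart and uses both for wear time: "If an unscheduled visit takes place between consecutive assessments multiple duration of wear values will be derived". SAP 4.6 lists wear beyond 3 days as a deviation for ActiV.A.C. (the SAP's name for the comparator) and for PICO with filler. For PICO without filler the listed limit is 7 days.

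Protocol 9.5 describes the resource to be captured as "personnel usage (number of personnel, and time, required for dressing change", with no restriction to scheduled visits.

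**The concern.** Item 38 claims to cover the whole study but adds up scheduled visits only. The work it leaves out depends on the arm by design: the protocol instructs it for tNPWT and for anyone with a filler, and not for PICO without filler. The t-test in SAP 4.12 would then compare scheduled-visit workload under the name of total workload. How often a dressing must be changed is one of the ways the devices can differ in staff time, and that part would be missing from the tested figure.

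**Working it through.** The documents give no expected value, SD or effect for personnel time, so there is no stated figure to reproduce. The check is a count of applications.

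**Does Study Visit include unscheduled visits?** No. Item 26 uses both terms within one set of formulas, and item 31 defines interventions from unscheduled visits alone. Item 38 names Study Visits only.

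**Inputs.** NPWT is applied at Study Visits 1-12 (SAP 2.1; study plan table), so item 38 counts at most 12 applications. Let *e* be the between-visit changes per week. All applications over 12 weeks = 12 × (1 + *e*), and the share omitted = *e* / (1 + *e*).

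| Pattern | *e* | All applications | Counted | Omitted |
|---|---|---|---|---|
| PICO, no filler, 7-day wear | 0 | 12 | 12 | 0% |
| One mid-week change | 1 | 24 | 12 | 50% |
| Wear of 3 days or less: ceil(7/3) − 1 | 2 | 36 | 12 | 67% |
| Wear of 2 days: ceil(7/2) − 1 | 3 | 48 | 12 | 75% |

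The range is needed because the texts do not settle *e*. Read literally, 9.1.7 could mean one change after 2-3 days. The next dressing would then stay on for 4-5 days, past the 3-day limit in SAP 4.6.

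**Between-arm effect.** Let *t_T* and *t_P* be person-minutes per application, and *e_T* and *e_P* the mean between-visit changes per week, for tNPWT and PICO.

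- Difference under item 38 = 12(*t_T* − *t_P*)
- Omitted difference = 12(*e_T t_T* − *e_P t_P*)

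The tNPWT-minus-PICO difference is understated whenever *e_T t_T* exceeds *e_P t_P*. If PICO without filler is worn for 7 days, a share *p* of PICO subjects use filler, *e* is the same for tNPWT and filler users, and minutes are equal (*t*), then the omitted difference = 12*et*(1 − *p*).

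**Illustration.** Minutes and filler use are assumptions. Results are per subject for *e* = 1, 2, 3:

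- *p* = 0: *t* = 10 gives 120, 240, 360 minutes; *t* = 20 gives 240, 480, 720; *t* = 30 gives 360, 720, 1080.
- *p* = 0.5: half of each.
- *p* = 1: zero.
- *p* = 1 with unequal minutes (20 tNPWT, 10 PICO): item 38 gives 12 × 10 = 120 minutes; all changes give 240, 360, 480.

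**Shorter PICO wear.** Protocol 4.2 reports a mean PICO wear of 4.6 days in a small mixed-wound study. That is 84/4.6 ≈ 18.3 applications. At 20 minutes in both arms, the omitted difference is (24 − 18.26) × 20 ≈ 115, (36 − 18.26) × 20 ≈ 355, or (48 − 18.26) × 20 ≈ 595 minutes, against 240, 480 and 720 at 7-day wear.

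**The case against.** **Rank.** Resource use is not among the listed primary, secondary or exploratory objectives, and the test sits under Other Data Summaries. This stands.

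**Visibility.** Change frequency is not hidden. Wear time counts unscheduled visits (item 26) and is compared by regression in SAP 4.11. SAP 4.7 summarises applications per subject. This stands: what is lost is the conversion of frequency into staff minutes.

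**Who does the work.** Subjects are told to complete the change. The documents do not say who performs it or whether anyone times it. The protocol asks for personnel and minutes at Study Visits, and the CRF is not available. A sum restricted to directly recorded visits may be deliberate. That is a fair reason for a different variable, but not for calling it the total throughout the study.

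**The instruction itself.** Protocol 9.1.3 and 9.1.4 give the 2-3 day instruction to filler users only, and 9.1.7 adds tNPWT. SAP 2.1 leaves changes to the investigator or the instructions for use. The 3-day limit in SAP 4.6 supports the wider reading for ActiV.A.C., but the texts differ.

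**Stronger readings the documents do not support.** A reader might infer that a difference of several hundred minutes would be reported as zero. That requires equal minutes per application, no PICO filler and 7-day PICO wear. Protocol 6.2 allows filler and gives 6 days for moderately exuding wounds. A reader might also infer that a wrong total would enter the economic analysis. Protocol 9.5 makes that analysis post hoc and conditional, and nowhere names item 38 as its input.

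**Conclusion.** The definition does not deliver what its name claims. For a full-course tNPWT or filler subject it counts 12 of 24-48 applications, omitting 50-75%. For PICO without filler at 7-day wear it omits none, and with shorter wear it omits some. The tested difference is understated as long as between-visit staff time is larger on tNPWT than on PICO, and the error then works against the sponsor's own device. The size in minutes cannot be computed from the documents, since it rests on minutes per application, PICO filler use and actual wear. With universal PICO filler use, equal change frequency and equal minutes, the omitted difference is zero. The 12-week counts assume no early closure or withdrawal.

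The defect is limited to a resource-use summary, but it is a stated rule that gives a wrong total and is cheap to correct.

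**What to change.** Redefine item 38 as the sum of personnel time over all NPWT applications, at Study Visits and at unscheduled dressing changes.

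- Where the Unscheduled Visit page holds number of personnel and minutes, use them.
- Where it does not, use the subject's mean personnel time per application multiplied by the number of applications, and state the assumption that an unscheduled change takes the same staff time as a clinic one. Items 26-27 already allow the applications to be counted. SAP 2.3.5 drops a dressing of unknown wear from the wear-time average, but it was applied and should stay in this count.
- If the Study-Visit-only sum is kept, label it *total personnel time at scheduled visits*, and neither test nor interpret it as total time. It remains a sum that varies with closure and withdrawal, so it should not be called a time per application either.

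Reconcile the 2-3 day instruction across Protocol 9.1.3, 9.1.4 and 9.1.7, and with the 3-day limit in SAP 4.6, so that the expected number of changes is clear.

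The cost is a few lines of SAP text. Direct recording would need two fields on the Unscheduled Visit page if they are not already there; the imputation route needs no new data.
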